7.1.2.6 Tumor Imaging and Assessment of Disease

Tumor imaging is strongly preferred to be acquired by computed tomography (CT). For the abdomen and pelvis, contrast-enhanced magnetic resonance imaging (MRI) may be used when CT with iodinated contrast is contraindicated, or when local practice mandates it. MRI is the strongly preferred modality for imaging the brain. The same imaging technique regarding modality, ideally the same scanner, and the use of contrast should be used in a participant throughout the study to optimize the reproducibility of the assessment of existing and new tumor burden and improve the accuracy of the assessment of response or progression based on imaging.

7.1.2.6.1 Initial Tumor Imaging

Initial tumor imaging will be performed as part of routine clinical management and must be performed within 28 days prior to the date of IP port placement. Routine imaging includes oral and IV contrasted CT of the chest/abdomen/pelvis. The site study team must review screening images to confirm the participant has measurable disease per RECIST 1.1.

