5.1.2 Participant Exclusion Criteria

Participants are excluded from the study if any of the following criteria apply:

- 1. A WOCBP who has a positive urine pregnancy test within 72 hours prior to infusion of treatment regimen (see Appendix 3). If the urine test is positive or cannot be confirmed as negative, a serum pregnancy test will be required. Note: in the event that 72 hours have elapsed between the screening pregnancy test and the first dose of study treatment, another pregnancy test (urine or serum) must be performed and must be negative in order for subject to start receiving study medication
- 2. Has received prior therapy with an anti-PD-1, anti-PD-L1, or anti-PD-L2 agent or with an agent directed to another stimulatory or co-inhibitory T-cell receptor (e.g., CTLA-4, OX-40, CD137).
- 3. Has received prior systemic anti-cancer therapy including investigational agents within 4 weeks prior to allocation. Any daily oral agent requires only a 2 week washout.
 - o Note: Participants must have recovered from all AEs due to previous therapies to ≤Grade 1 or baseline. Participants with ≤Grade 2 neuropathy may be eligible.
 - Note: If participant received major surgery, they must have recovered adequately from the toxicity and/or complications from the intervention prior to starting study treatment.

^a Criteria must be met without erythropoietin dependency and without packed red blood cell (pRBC) transfusion within last 2 weeks.

^b Creatinine clearance (CrCl) should be calculated per institutional standard.

4. Has received prior radiotherapy within 2 weeks of start of study treatment. Participants must have recovered from all radiation-related toxicities, not require corticosteroids, and not have had radiation pneumonitis. A 1-week washout is permitted for palliative radiation (≤2 weeks of radiotherapy) to non-CNS disease.

- 5. Patients with previous pelvic radiation therapy.
- 6. Has received a live vaccine within 30 days prior to the first dose of study drug. Examples of live vaccines include, but are not limited to, the following: measles, mumps, rubella, varicella/zoster (chicken pox), yellow fever, rabies, Bacillus Calmette–Guérin (BCG), and typhoid vaccine. Seasonal influenza vaccines for injection are generally killed virus vaccines and are allowed; however, intranasal influenza vaccines (e.g., FluMist®) are live attenuated vaccines and are not allowed.

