5.2.1 Timing of Dose Administration

Trial treatment should be administered on day 1 and 2 of each cycle after all procedures/assessments have been completed as detailed on the Trial Flow Chart (Section 6.0). Trial treatment may be administered up to 3 days before or after the scheduled day 1 of each cycle due to administrative reasons.

All trial treatments will be administered on an outpatient basis.

Cisplatin administration

As a part of our institutional standard of care, all patients will receive 4 neoadjuvant cycles (1 cycle = 21 days) 50 mg/m² cisplatin administered over 1 hour (capped at 100 mg total dose per infusion), on day 1 (Monday) of cycles 1, 2, 3, and 4, and up to 2 adjuvant cycles of IPC.

Prehydration for cisplatin

Five hundred to one thousand milliliters of 0.9% sodium chloride will be given IV to prehydrate prior to infusion of cisplatin IP. Post IPC hydration with an additional liter of 0.9% sodium chloride will also occur.

Premedications for cisplatin

Benadryl 50mg IV on Day 1

Palonosetron (Aloxi) 0.25 mg IV X 1 dose

Fosaprepitant (Emend) 150 mg IV in Total Volume 150 mL 0.9% sodium chloride to infuse over 20 minutes

Note: The above premedications may be adjusted at the investigator/sub-investigator's discretion based upon institutional guidelines and the patient's medical status.

Intraperitoneal cisplatin administration

Cisplatin is generally given into an established, semi-permanent access device implanted with a catheter attached to a port in the peritoneal cavity. Five hundred milliliters to one liter of cisplatin containing fluid is infused per institutional standards, no less than 45 minutes, followed by an additional 500 to 1000 mL of 0.9% sodium chloride, where feasible, to a total of 2000 mL IP ensuring adequate distribution of the fluid. Ideally, a total of two liters of fluid is instilled into the abdominal cavity if tolerated.

Cisplatin will be administered on day 1 (Monday) of each 21-day cycle by IP infusion at 50 mg/m² over 1 hour. Each patient will receive 4 neoadjuvant cycles and 2 adjuvant cycles.

No attempt will be made to retrieve the infusate. However, if a large amount of ascites is present, ascites may be drained by paracentesis or accessed by port prior to instillation of the drug.

Post hydration after cisplatin

One liter of 0.9% sodium chloride will be given intravenously. If fluid overload is of concern, patient may be treated with Lasix or Mannitol as needed to maintain urine output.

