5.3 Randomization or Treatment Allocation

Single arm phase II study, no randomization

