6.0 TRIAL FLOW CHART

6.1 Study Flow Chart

Parameter/ Week	Pre- Treatment ^A	2	5	7	8	11	13	15-16	19	22	Safety Follow-up	31 ^H IP Cath removal	Survival Follow- Up
Cycle		1	2	2	3		4		5	6	4-6 weeks Post Treatment End	End of Study	Every 12 weeks (+/- 4)
Informed Consent	X												1 . , 1 ,
Inclusion/Exclusion Criteria	X												
Baseline Pregnancy Test – see Appendix 3	X												
Baseline TSH, T3/T4	X												
Demographics & Medical History	X												
Prior and Commitment Medication Review	X	X	X		X	X	X		X	X	X		
Full Physical Examination ^B	X						X#						
Directed Physical Examination		X ^I	X		X	X			X	X	X		
Vital signs ^C	X	X	X		X	X	X#		X	X	X		
Height and Weight	X												
ECOG Performance Status	X	X ^I	X		X	X	X#		X	X	X		

Parameter/ Week	Pre- Treatment ^A	2	5	7	8	11	13	15-16	19	22	Safety Follow-up	31 ^H IP Cath removal	Survival Follow- Up
Cycle		1	2	2	3		4		5	6	4-6 weeks Post Treatment End	End of Study	Every 12 weeks (+/- 4)
Adverse Events			X		X	X	X#		X	X	X		.,, .,
CBC with differential, Mag, Phos, LDH, uric acid, CA- 125, and CMP ^{D,}	X	X ^I	X		X	X	X		X	X	X		
Urine analysis	X	X	X		X	X	X		X	X	X		
PT/INR and aPTT	X												
EKG	X	X ^I											
Tumor size CT imaging	X*			X*			X*				X		X*
IP catheter and tumor biopsy	X											X	
Tumor debulking								X					
Cisplatin (IP)		X	X		X	X			X	X			
IP Rintatolimod		X	X		X	X			X	X			
IV Pembrolizumab		X	X		X	X			X	X			
Peritoneal washes ^E	X ^G	X	X		X	X		X	X	X	X	X	

Parameter/ Week	Pre- Treatment ^A	2	5	7	8	11	13	15-16	19	22	Safety Follow-up	31 ^H IP Cath removal	Survival Follow- Up
Cycle		1	2	2	3		4		5	6	4-6 weeks Post Treatment End	End of Study	Every 12 weeks (+/- 4)
Blood (30-40 cc) drawn for in vitro assays ^F	X	X	X		X	X		X	X	X	X	X	
Survival Status **													X

46

A. 28 day screening period to C1D1 unless otherwise noted.

B: Physical examination will be performed by the attending physician or fellow/APP (advanced practice providers).

C: Vital signs (temperature, blood pressure, pulse rate, and respiratory rate) will be taken prior to the administration of each dose of trial treatment.

D: Glucose, BUN, creatinine, sodium, potassium, chloride, CO₂, calcium, total protein, albumin, alkaline phosphatase, AST, ALT, total bilirubin,

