After placement of IP port, ideal start time is days 1-14 after port placement with no more than 21 day window unless wound infection or complications precluding start of treatment. To be approved by PI. Additionally, there is a window of \pm 3 days available for scheduling/rescheduling the remainder of treatments and/or procedures at the discretion of the Subinvestigator, and as discussed with the Investigator if a course is missed or a subject's treatment and/or testing day(s) need to be rescheduled due to the subject's inability to comply with the study calendar (this includes but is not limited to: hospitalizations, business, vacation plans, travel from long distances for study treatment, in advance of the scheduled date to allow ready access to the result(s), reduce financial burden on the subject [i.e. non-UPMC insurance coverage] or reduce travel inconvenience, illness, transportation issues, holidays, family emergencies, etc.).

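### The baseline CT is timed from port placement rather than from first dose, so a compliant RECIST baseline can be 42 to 49 days old when treatment starts

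*Combined protocol and SAP*

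**What the plan says.** **Baseline scan.** Section 7.1.2.6.1 (Initial Tumor Imaging) states that the scan "must be performed within 28 days prior to the date of IP port placement". The site uses it to confirm measurable disease by RECIST 1.1. Footnote A to the flow chart in Section 6.1 gives a "28 day screening period to C1D1 unless otherwise noted". The imaging footnote under the same chart sets no other baseline window.

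**Gap to first dose.** The note after the flow chart reads: "ideal start time is days 1-14 after port placement with no more than 21 day window unless wound infection or complications", with exceptions approved by the PI. Section 5.2.1 adds a tolerance: "Trial treatment may be administered up to 3 days before or after the scheduled day 1 of each cycle".

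**On-study scans.** Section 7.1.2.6.1 (Tumor Imaging During the Study) places these scans 49 and 91 days after port placement, each with a 7-day margin. They stay on calendar days even when cycles start late.

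**Endpoint.** Section 8.1 makes objective response at 13 weeks the primary endpoint and judges it against a historical rate of about 45%. There is no control arm.

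**Earlier therapy.** Inclusion 4 admits patients who have had other lines since their last platinum. Exclusion 3 in Section 5.1.2 bars systemic treatment "within 4 weeks prior to allocation. Any daily oral agent requires only a 2 week washout". Section 5.3 reads "Single arm phase II study, no randomization", and no section defines an allocation date. Section 5.5.2 prohibits systemic cancer chemotherapy and biological therapy throughout screening and treatment.

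**The concern.** Response at week 13 is the change from the baseline CT. Whatever happens to the tumour between that CT and the first dose is therefore counted as if the regimen had caused it. Growth before dosing hides part of a real response. Shrinkage carried over from earlier therapy is credited to the study drugs. With no control arm, nothing cancels either error, and the result is read against a fixed historical figure.

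The two windows are also not equivalent. A site that follows Section 7.1.2.6.1 as a specific exception to footnote A, and a site that applies both, would work to different limits on the age of the baseline. Nothing requires a repeat CT before C1D1, and nothing requires the baseline CT to follow the last dose of prior therapy.

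**Working it through.** The plan states no figure for the age of the baseline CT, so there is none to reproduce. The check has four steps.

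**1. Age of the CT at first dose.** Inputs: 28 days (Section 7.1.2.6.1) and a gap of 14 or 21 days (note to the flow chart).

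- End of the ideal window: 28 + 14 = 42 days.
- Stated limit: 28 + 21 = 49 days.
- If the 3-day tolerance of Section 5.2.1 is added: 49 + 3 = 52 days. With wound infection or complications no cap is given.
- If footnote A is applied as well: at most 28 days.

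**2. Share of the measured interval without study treatment.** Take the CT on day -28 and C1D1 on day 21, counted from port placement.

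- Baseline to nominal week 13: 28 + 91 = 119 days, of which 49 precede treatment (49/119 = 41%).
- Baseline to nominal week 7: 28 + 49 = 77 days, of which 49 precede treatment (49/77 = 64%).

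**3. Illustration of what growth would do.** The documents give no growth rate. I assume spherical growth with a volume doubling time (DT) of 60 to 120 days. Diameter growth = 2^(days / (3 × DT)). A partial response is a 30% fall from the recorded baseline, so the true shrinkage needed from first dose = 1 - 0.70 / growth.

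| CT age | Growth, DT 60 | Shrinkage needed | Growth, DT 120 | Shrinkage needed |
|---|---|---|---|---|
| 28 days | 1.114 | 37.2% | 1.055 | 33.7% |
| 42 days | 1.176 | 40.5% | 1.084 | 35.4% |
| 49 days | 1.208 | 42.0% | 1.099 | 36.3% |

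Moving from a 49-day to a 28-day limit lowers the hurdle by about 3 to 5 percentage points.

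**4. Prior therapy after the CT.** This depends on what allocation means. With the CT on its earliest day and gaps of 14 / 21 days, exclusion 3 taken alone would let treatment end after the CT by these amounts:

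- Allocation read as C1D1: 28 / 35 days for a daily oral agent, 14 / 21 days for other systemic therapy.
- Allocation read as port placement: 14 / 14 days for an oral agent, 0 for other systemic therapy.
- Allocation read as registration before port placement: none for other systemic therapy; for an oral agent, only if registration is less than 14 days before port placement.

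Section 5.5.2 then cuts across this. If screening is the 28 days before C1D1, the agents it covers cannot be taken in that time. The longest overlap for them is 42 - 28 = 14 or 49 - 28 = 21 days, and it is zero if the CT itself falls within screening. A 2-week oral washout counted from C1D1 would allow dosing between 28 and 14 days before C1D1, a period in which Section 5.5.2 forbids the agents it covers.

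**The case against.** The strongest reply is that footnote A already limits screening to 28 days before C1D1, so a site that obeys both rules never has an older CT. This does not settle the matter. Footnote A yields where something else is noted, and Section 7.1.2.6.1 is a specific, mandatory rule with a different anchor. Either it overrides footnote A or the two conflict. In both cases the text needs repair.

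Port placement is also a sensible anchor in one respect: measurable disease should be confirmed before surgery. That stands. The initial procedure includes a biopsy, ideally of more than 2 grams (Section 2.1), so a CT repeated afterwards would be a baseline taken after tumour tissue was removed. The remedy should not call for one.

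It is fair, too, that 42 and 49 days are permitted maxima, that the documents give no typical gap, and that the doubling times are assumed.

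Two stronger readings are tempting:

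- A reader might infer that a patient may take an oral cancer drug for up to 35 days after the baseline CT. That needs allocation to mean C1D1, the longest stated gap and the earliest CT, and for the agents covered by Section 5.5.2 it conflicts with that section's ban during screening.
- A reader might infer that patients would already meet the progression threshold at first dose, since 1.208 is growth of 20.8%. That occurs only at the corner of 60-day doubling and 49 days; at 42 days the figure is 17.6%. Appendix 4 also requires an absolute increase of 5 mm, which at 20.8% means a baseline sum of about 24 mm or more (5 / 0.208). Progression at week 7 would further require almost no shrinkage after two cycles.

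**Conclusion.** The point holds for the baseline CT. Under Section 7.1.2.6.1 a compliant baseline can be 42 to 49 days old at first dose, and longer with complications, while footnote A points to 28. At the extreme, 41% of the interval over which week-13 response is measured contains no study treatment. These figures follow from the documents' own windows, with no growth assumption.

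The effect on the response rate cannot be sized from the documents, and its direction is not fixed: pre-treatment growth lowers the apparent rate, and residual prior-therapy effect raises it. The shrinkage figures (36-42% against 34-37%) are an illustration that rests on the assumed doubling time and on the latest permitted schedule.

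On prior therapy the documents support a narrower conclusion. Exclusion 3 counts from an undefined date, and its oral-agent washout does not fit with the ban during screening in Section 5.5.2. They do not show a fixed amount of overlap, and they do not tell a reader which anchor the sponsor intended.

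**What to change.** In Section 7.1.2.6.1 (Initial Tumor Imaging), require the baseline CT to be taken before port placement, within 28 days before C1D1, and after the last dose of prior anti-cancer therapy. One schedule that meets this without an extra scan is a CT no more than 14 days before port placement with C1D1 within 14 days after it (14 + 14 = 28). If C1D1 is planned at the 21-day limit, the CT must fall within 7 days before port placement (28 - 21 = 7).

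If C1D1 slips, keep the pre-operative CT as the baseline and record the CT-to-C1D1 interval. In Section 8.2, add a sensitivity estimate of the response rate, with its exact 90% limits, that excludes patients whose interval exceeds 28 days. The interval is fixed before first dose, so the exclusion does not depend on response. Patients with long delays may differ in other ways, however, so this estimate should be read beside the primary one and should not replace it.

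Separately, the sponsor should reconcile exclusion 3 with Section 5.5.2 and name a defined date in place of allocation, there and in the ECOG window of inclusion 10. Which date and which washout apply is for the sponsor to decide.

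The cost is a protocol wording change, one recorded interval, one extra analysis and tighter scheduling of the CT, port placement and first dose.

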7.1.2.6.1 Tumor Imaging During the Study

The first on-study imaging assessment should be performed at 7 weeks (49 days ± 7 days) from the IP port placement, again at 13 weeks (91 days ± 7 days) prior to interval surgery, after 4-6 weeks after treatment completion. Subsequent tumor imaging should be performed every 12 weeks (84 days ± 7 days) or more frequently if clinically indicated. After 31 weeks (245 days ± 7 days), participants who remain on treatment will have imaging performed every 12 weeks (84 days ± 7 days). Imaging timing should follow calendar days and should not be adjusted for delays in cycle starts. Imaging should continue to be performed until disease progression is identified by the Investigator.

Objective response should be confirmed by a repeat imaging assessment. Tumor imaging to confirm PR or CR should be performed at least 4 weeks after the first indication of a response is observed. Participants will then return to regular scheduled imaging every 12 weeks, starting with the next scheduled imaging time point. Participants who receive additional imaging for confirmation do not need to undergo the next scheduled tumor imaging if it is less than 4 weeks later; tumor imaging may resume at the subsequent scheduled imaging time point.

Per iRECIST (Section 9.2.1.6), disease progression should be confirmed by the site 4 to 8 weeks after first radiologic evidence of PD in clinically stable participants. Participants who have unconfirmed disease progression may continue on treatment at the discretion of the Investigator until progression is confirmed by the site provided they have met the conditions detailed in Section 9.2.1.6. Participants who receive confirmatory imaging do not need to undergo the next scheduled tumor imaging if it is less than 4 weeks later; tumor imaging may resume at the subsequent scheduled imaging time point, if clinically stable. Participants who have confirmed disease progression by iRECIST, as assessed by the site, will discontinue study treatment. Exceptions are detailed in Section 9.2.1.6.

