2.0 TRIAL DESIGN

2.1 Trial Design

This is a phase II single arm efficacy/safety trial that will evaluate the effectiveness of combining intensive locoregional intraperitoneal (IP) chemoimmunotherapy of cisplatin with IP rintatolimod (TLR-3 agonist) and IV infusion of the checkpoint inhibitor pembrolizumab (IVP) for patients with recurrent platinum-sensitive ovarian cancer (OC).

Patient cohort

This trial will enroll up to 45 patients; eligibility criteria include patients at first or second recurrence previously diagnosed with platinum-sensitive ovarian/fallopian tube carcinoma or primary peritoneal carcinomatosis. Platinum-sensitive OC is defined as patients with a treatment-free interval greater than 6 months. Patients must have at least one peritoneal lesion, measurable by CT/MRI scan. Patients will be allowed if RECIST 1.1 criteria is met for measurable retroperitoneal lesions if there also is the presence of peritoneal lesions during laparoscopy. The lesion should be large enough for biopsy and resection, ideally to yield greater than 2 grams of tumor for immunoassays. If biopsy is insufficient or not feasible during laparoscopy, patients may be allowed to proceed at the discretion of the PI if there are otherwise measurable lesions. All epithelial invasive histologies are included in this phase II design.

Patients will receive a total of six treatment cycles, at 3-week intervals (Schema 1, Section 2.2). We will use an IP neoadjuvant approach, followed by interval cytoreduction (usually laparoscopically) of residual tumor. The decision to perform interval cytoreductive surgery is at

the discretion of the treating physician. Cytoreduction will occur approximately 4 weeks after the fourth treatment cycle. Post-surgery we will consolidate with 2 additional courses of same chemo-immunotherapy regimen. Catheter will be removed 12 weeks after the last treatment. All surgical procedures, if done laparoscopically, are outpatient and will yield up to three serial biopsies of the tumor sites: 1) at catheter placement; 2) at interval cytoreduction which consists of removal of any visible tumor sites and the site biopsied initially whether tumor is present or not; 3) at catheter removal, when site of first tumor biopsy will be re-biopsied for pathologic response.

[figure not shown]
5

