3.0 OBJECTIVE(S) & HYPOTHESIS(ES)

3.1 Primary Objective(s) & Hypothesis(es)

(1) **Objective:**

This phase II trial will consist of up to 45 evaluable patients to specifically define the clinical efficacy and impact on immunologic efficacy endpoints of IP cisplatin/rintatolimod and IV pembrolizumab. Primary clinical efficacy endpoint will be objective response rate by RECIST

6

1.1 criteria at 13 weeks (CT imaging at 7 weeks and 13 weeks) as compared to historical controls. The trial schema encapsulates a trial design similar to our recent phase I SPORE trial (UPCI 11-128/NCT02615574, [name] - Clinical PI; [name]- Translational PI) in which intraperitoneal cisplatin and rintatolimod was well tolerated and induced favorable immune response on interim analysis.

The strategy of combining pembrolizumab with IP cisplatin/rintatolimod is to induce cell death and cell damage of the peritoneal tumor implants with chemotherapy followed by locoregional and systemic modulation of innate and adaptive immune effectors to further promote immune clearance of remaining tumor.

Objective/Pathologic Response

Imaging will be performed at baseline, two weeks after cycle 2 and cycle 4 for objective responses by RECIST 1.1 criteria. Imaging will again be performed 4-6 weeks after completion adjuvant chemotherapy for baseline post treatment. Between 2 months after successful completion of the trial, the IP port will be removed laparoscopically. During the IP port removal, a second-look treatment effect evaluation and biopsy for pathologic response will be performed.

Disease Progression

Progression during trial will be assessed by iRECIST. If there is confirmed progression prior to interval surgery, patients will not undergo interval surgery, just IP port removal and biopsy after confirmed progression by iRECIST. Patients will be followed for 3 years or until recurrence after completing treatment to determine time to progression (TTP), ratio of progression-free interval (PFI) as compared to their initial PFI, and survival will be a secondary efficacy endpoint. Follow-up data will be used to estimate progression-free and overall survival at 3 years.

Biological Endpoints

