The primary endpoint is the objective response rate (rate of CR+PR by RECIST 1.1) at 13 weeks. Based on Ten Tije and Wils et al, the intent-to-treat objective response rate for IP cisplatin alone in platinum-sensitive recurrent ovarian cancer was approximately 45% 51 . An increase from 45% to 65% among response-evaluable patients would be of sufficient interest to warrant further study of the addition of rintatolimod and pembrolizumab in the presence of an acceptable safety profile. An optimal Simon two stage design with $\alpha = \beta = .10$ has been selected that will require 20 patients in the first stage and 25 in the second. In the first stage, 12 patients must have a response (PR or CR) in order to continue to the second stage. If the trial continues to the second stage and accrues 25 more patients and there are 25 or more patients with an objective response among the total of 45 treated, the study will be considered successful at demonstrating increase efficacy compared to cisplatin alone. The probability of early termination if the response rate is 45% is .59.

Continuous Monitoring of RLTs during the Study

Subject safety will be monitored continuously using Bayesian methods. If the posterior probability is .80 or greater that 30% or more of treated subjects experience a treatment related RLT as defined above, the RLT rate would be unacceptable and the study will be suspended pending review by the DSMC. This posterior probability will be calculated from the study's accumulating data and a weakly informative prior distribution. If π denotes a random variable representing the proportion of subjects who will experience a treatment related RLT, we assume π has a beta distribution with parameters a = 1.2 and b = 2.8 which assumes a mean of 30%. The table below describes the number of RLTs per number of treated patients that would trigger suspension. The table also shows the posterior probability that the RLT rate exceeds 33% and the binomial probability associated with the decision for an assumed 33% RLT rate.

Table 8: Number of RLTs per Number of Patients Treated Needed to Trigger Suspension

Subjects	Treatment-Related RLTs	$PP(\pi > 30\%)*$	$Pr(X \ge r p = .30)$
6	4	.903	.070
9	5	.904	.099
12	6	.890	.118
15	7	.880	.131
17	8	.903	.105
20	9	.896	.113
23	10	.891	.197
26	11	.886	.125
29	12	.883	.129
32	13	.880	.133

35	14	.877	.135
38	15	.876	.137
41	16	.874	.138
44	17	.873	.139

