8.2 Statistical Analysis Plan

Proposed Data Analysis Primary Objectives

Objective response rate and progression-free based on RECIST 1.1 criteria (RC) will be estimated with 90% confidence intervals. The objective response rate (ORR) will be estimated by the proportion of subjects with the best response of complete response (CR), or partial response (PR) by RC, with corresponding exact 90% confidence limits being reported.

Proposed Data Analysis Secondary Analysis

The progression-free survival (PFS) will be measured from the initial date of the study treatment to the date of documented tumor progression using RC, or the date of death in the absence of tumor progression. PFS will be estimated by the Kaplan-Meier method with Greenwood 90% confidence intervals

Within-patient changes in CD8+ cells will be measured in tumor tissue and in peritoneal fluid at weeks 1,8, and 12. Mixed linear models will be used to estimate changes from baseline.

An assessment of the association among immune parameters, and ORR will be conducted. Endpoints for analysis include (CTL, NK- and Th1 cells) in the peritoneal fluid and resected residual tumor mass The panel of immune parameters will be tested for association with objective response with the Jonckheere-Terpstra test for trend by ordering response 1-4 for PD, SD, PR and CR, respectively. Significant association will be adjusted for initial tumor grade, and the interval between initial diagnosis of OC and protocol accrual. To guard against false positive results, the estimated false discovery rate will be calculated by the method of Benjamini and Hochberg (J. R. Statist. Soc. B Vol 57, No 1, 289-300, 1995).

HCC 18-087 Version Dated 5-20-2021

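### The plan does not say whether a response first seen on the week-13 CT must be confirmed, and in operated patients the 4-week repeat scan nominally falls after debulking

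*Combined protocol and SAP*

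**What the plan says.** Three places bear on which responses are counted.

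- Section 8.1: "The primary endpoint is the objective response rate (rate of CR+PR by RECIST 1.1) at 13 weeks". Section 3.1 agrees and names the CT scans at weeks 7 and 13. Neither mentions confirmation.
- Section 8.2 estimates the response rate as the "proportion of subjects with the best response of complete response (CR), or partial response (PR) by RC". It gives neither a time limit nor a confirmation requirement.
- Section 7.1.2.6.1 (Tumor Imaging During the Study): "Objective response should be confirmed by a repeat imaging assessment". It then sets the gap: "Tumor imaging to confirm PR or CR should be performed at least 4 weeks after the first indication of a response is observed".

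Two places fix the surgery. Section 2.1 says: "Cytoreduction will occur approximately 4 weeks after the fourth treatment cycle". It describes the operation as taking out whatever tumor can be seen. The flow chart in Section 6.1 enters "Tumor debulking" in the column for weeks 15-16. Sections 2.1 and 3.3 leave the decision to operate to the treating physician.

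On progression, Section 3.1 says: "If there is confirmed progression prior to interval surgery, patients will not undergo interval surgery". Section 7.1.2.6.1 asks that progression be confirmed 4 to 8 weeks after it is first seen.

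**The concern.** Only two on-study scans come before surgery. A response seen at week 7 can be confirmed at week 13. A response first seen at week 13 has no scheduled pre-surgery scan left to confirm it, and the 4-week gap runs past the planned operation. A scan after tumor has been removed will tend to look like a response whatever the drugs did.

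The trial is open-label with one arm and is decided by a fixed count, 25 or more responders in 45, with an earlier look at 20 patients. Analysts following different sections could defend different counts from the same patients:

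- the week-13 reading as it stands (8.1);
- only responses confirmed before surgery (7.1.2.6.1, with surgical scans disallowed);
- any response at any time, including after debulking (8.2 read literally).

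The second lowers the count and the third can raise it. A choice made after the scans are known could decide the result.

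**Working it through.** **Timeline.** Section 7.1.2.6.1 counts scan days from port placement, and the flow chart uses the same week numbers.

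- Week-7 scan: day 49 ± 7, so days 42 to 56.
- Week-13 scan: "again at 13 weeks (91 days ± 7 days) prior to interval surgery", so days 84 to 98.
- Cycle 4 dosing: week 11 in the flow chart, day 77.
- Surgery: 77 + 28 = day 105 (week 15) by Section 2.1, and weeks 15-16 (days 105 to 112) by the flow chart. The ± 3-day scheduling window below the flow chart extends this to day 115.
- Next scheduled scan: 4-6 weeks after treatment ends. With the last dose at week 22, that is about weeks 26-28.

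A response first seen at week 7 is confirmable at week 13, because even at the window edges 84 − 56 = 28 days. A response first seen on day 91 is confirmable from 91 + 28 = day 119 (week 17), which is 1 to 2 weeks after surgery at weeks 15-16.

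Exceptions: a scan on day 84 allows confirmation on day 112, the last nominal surgery day. A 14-day slip in cycle 4 moves surgery to 77 + 14 + 28 = day 119, while scan dates stay fixed to the calendar. Patients who are not operated on can be rescanned at week 17. In the other direction, if cycle 1 starts on day 7 after port placement, cycle 4 falls on day 70 and surgery by Section 2.1 on day 98, which widens the gap.

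**The plan's own design.** Inputs from Section 8.1: rates of 45% and 65%, 20 + 25 patients, success at 25 or more, α = β = 0.10, stated early-termination probability .59. With q the countable response rate and c the stage-1 cut,

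P(success) = Σ (x = c to 20) P[Bin(20, q) = x] × P[Bin(25, q) ≥ 25 − x].

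A search for the optimal Simon design returns c = 10 with 25 of 45: early termination 0.591, α 0.090, power 0.900. That matches the stated .59. The written cut of 12 gives early termination 0.869, α 0.053 and power 0.746. This is a separate matter; the calculation below uses c = 10 because it reproduces the stated properties.

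**If confirmation before surgery were required.** Let f be the share of responders first seen at week 13 (not in the documents, so a range is shown) and s the share operated on. Section 3.3 reports that two thirds completed interval debulking in the earlier phase I study; s = 1 is the upper limit. Then q = 0.65 × (1 − f × s). For example, with f = 10% and s = 2/3, q = 0.65 × (1 − 0.0667) = 0.607.

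| f | q, s = 2/3 | power | q, s = 1 | power |
|---|---|---|---|---|
| 0 | 0.650 | 0.90 | 0.650 | 0.90 |
| 10% | 0.607 | 0.76 | 0.585 | 0.67 |
| 25% | 0.542 | 0.45 | 0.488 | 0.20 |
| 50% | 0.433 | 0.06 | 0.325 | 0.001 |

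With the written cut of 12 and s = 2/3, power is 0.75, 0.58 and 0.30 at f = 0, 10% and 25%.

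**If the week-13 reading counts unconfirmed.** q stays at 0.65 and nothing changes: α 0.090, power 0.900.

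**Progression.** First seen at week 7, the 4-8 week window is weeks 11-15 and contains the week-13 scan. First seen at week 13, the window is weeks 17-21, after planned surgery.

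**The case against.** The best defence is that the primary endpoint never depended on the confirmation rule. Sections 3.1 and 8.1 fix it at 13 weeks, and a scan at week 17 cannot be part of a rate at week 13. Where the protocol wants confirmation it says so: Section 5.6 refers to a confirmed complete response when discussing stopping treatment, and Section 3.1 refers to confirmed progression. The word is absent from Sections 8.1 and 8.2. Section 7.1.2.6.1 says only that response should be confirmed and attaches no consequence if it is not. Much of this stands. It makes the unconfirmed week-13 response the most natural reading. It does not settle the matter, because Section 7.1.2.6.1 uses the same term, objective response, and Section 8.2 departs from 8.1 by dropping the time limit.

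A reader might also infer that a week-13 response can never be confirmed. The documents do not support that: surgery is discretionary, the windows just touch at week 16, and cycle delays move surgery but not scans. These exceptions are a matter of chance, however, and are not a rule for counting responders.

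On progression, the defence is that Section 3.1 says only what follows if progression is confirmed before surgery. It does not promise that every progression can be. Clinically unstable patients stop treatment under Table 5 without waiting for confirmation. Progression first seen at week 13 also adds nothing to the responder count, so this is a side issue.

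**Conclusion.** The point holds as an unresolved conflict between Sections 7.1.2.6.1, 8.1 and 8.2 over which responses count. It affects patients whose response is first seen at week 13 and who are then debulked. Under 8.2 read literally, it also affects anyone whose first apparent response is on a post-surgery scan. The documents give no figure for either group.

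The size depends on the reading. Under 8.1 as most naturally read, there is no loss. Under required pre-surgery confirmation, power falls from 0.90 to 0.76 at 10% late responders and 0.45 at 25%, assuming two thirds are operated on, a true rate of 65% and the 10-of-20, 25-of-45 design. Under 8.2 read literally, surgical effect could raise the count by an amount that cannot be estimated from the documents.

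A reader might infer that the trial is badly underpowered. For instance, if 30% of responders were both late and debulked, the countable rate would be 0.65 × 0.70 = 45.5%, and the chance of 25 or more in 45, ignoring stage 1, would fall from 93% to 11%. The documents do not support that as a finding. It takes the strictest reading, and with two thirds operated on it needs 0.30 ÷ (2/3) = 45% of responders to be first seen at week 13, for which there is no evidence either way.

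The text should still be settled before responders are counted, because the 25-of-45 decision rests on it.

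**What to change.** - **Sections 8.1 and 8.2:** define the primary endpoint in the same words, as CR or PR by RECIST 1.1 on scans up to and including the pre-surgery week-13 CT, with no later confirmation required. As worded, this counts a week-7 response that is lost by week 13. If status at week 13 is meant, say so.
- **Post-surgery scans:** state that no scan after interval surgery may create, confirm or refute a response for the primary count.
- **Section 7.1.2.6.1:** align the response-confirmation text so that it does not govern the primary count.
- **Supportive estimate:** report response at week 7 maintained at week 13 as a confirmed rate.
- **Timing:** apply the same definition at the 20-patient look. If that count has already been taken, record which rule was used.
- **Progression:** reconcile the Section 3.1 sentence on confirmed progression before surgery with the 4-8 week window in Section 7.1.2.6.1 for progression first seen at week 13. How this is resolved is for the clinical team.

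The cost is wording only, with no added scan or patient. The downside is that the primary response rate is explicitly unconfirmed, which is somewhat less conservative and must be stated in the report.
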